## 10.3 Approach

### 10.3.1 Feasibility

The PI has in-depth experience researching kinematic outcomes related to falls in both cross-sectional and longitudinal studies of persons with PD and healthy older adults (Aim #1). Our preliminary studies have recently demonstrated improvements in functional mobility in a small sample of persons with mild-to-moderate PD undergoing this intervention (n=5). A statistically significant improvement was found in the Timed Up and Go (TUG) score (a measure of balance and mobility) from baseline to the mid-point assessment (-2.1 seconds, p=.035). Our preliminary data also demonstrate a clinically meaningful effect of the intervention with an effect size of  $d=0.66$ . Further, our preliminary data also suggests that of these 5 individuals tested thus far, 3 had primary deficits in anticipatory postural control adjustments at baseline according to the miniBEST test. This data will be used to guide our hypothesis-driven Aim #1.

Based on our recent postural control studies following an 18 week rehabilitation program^30 with no participant dropout, no difficulties are expected in recruitment and retention of PD participants for the proposed longitudinal exercise studies.

### 10.3.2 Health Disparities in PD in Caldwell, Canyon County, ID

Treatment disparities and access to resources for persons with PD are prevalent across healthcare settings. Specifically, resources for exercise and physical therapy are extremely limited in Canyon County due to the general health disparities in this region. We have specifically chosen to host our community-based exercise intervention in Canyon County because of its traditionally sparse access to healthy living resources. The Caldwell, Canyon County YMCA serves all of the western Treasure Valley region, where the average adult is less likely to be physically active than any other region of the valley. Several factors may be involved in these differences, including less access to safe and affordable recreation opportunities such as parks, green spaces, and community recreation centers across the region, less access to healthy foods, and higher rates of poverty in Canyon County as compared to Boise. Our intention is to provide our community-based intervention in this area specifically to increase access to healthy living resources for persons with PD in Caldwell and Canyon County, ID.

### 10.3.3 Research Design

Participants (aged 50 – 65; either sex, all ethnicities) will be recruited from local hospitals and clinics by various means, including physician referral or by response to flyer advertisements (see section 10.3.5). Potential participants will be screened over the phone regarding their possible inclusion in the study (see inclusion/exclusion criteria below). Among other things, participants will be asked if they have received a medical diagnosis of idiopathic PD from a neurologist, and if they have been medically cleared to participate in exercise by a physician.

On day one, participants will come to the Exercise Science laboratory at Idaho State University in Meridian. The PI will obtain informed consent and will complete patient screening according to our IRB approved research plan. Participants will be verbally asked for demographic information including name, contact information, ethnicity, age, gender, weight, height, and number of falls experienced over the past 3 months. Subjects will also take the Montreal Cognitive Assessment, which is a brief screening tool that provides a quantitative assessment of cognitive impairment. The Hoehn & Yahr scale will be used to identify Parkinson's disease stage. Participants meeting the inclusion criteria will be enrolled in the study and will undergo the baseline outcome assessments, which are described in the Section 10.3.4 below.

The intervention will take place at the Caldwell YMCA and consist of 12 weeks of exercise, guided by four certified personal trainers at the YMCA who are trained to work with individuals with neurologic conditions such as PD. All trainers have been trained to safely and effectively perform the balance activities that will be employed throughout the program. The head trainer has received a specialty certification in the boxing training program utilized in this study. A version of the proposed exercise program has been validated in a group of persons with PD previously. Our incorporation of balance training activities into the program introduces a novel and essential ingredient for fall reduction to the program.

Each session will begin with a 10-minute warm-up of breathing and stretching exercises for major muscle groups in the trunk and extremities. This will be followed by a 45- to 60-minute circuit training regimen of function, balance, and non-contact boxing activities that alternate between 3-minute training bouts and 1-minute rest breaks. The functional training will incorporate activities for whole-body fitness and calisthenics, such as push-ups and reaching tasks that are tailored to each participant's capability, along with boxing ring work, which focuses on footwork and agility drills. The balance training activities will focus on tasks in the following areas: quiet stance, anticipatory postural adjustments, reactive postural adjustments, and dynamic

postural control (Table 1). Participants will be placed into groups for this section of the training so that each individual is assigned to work on activities focused on their area of greatest deficiency in the four balance domains. Each domain will be overseen by a specific trainer to ensure safety and continuity of the balance training within each group. The boxing activities will include punching heavy bags, speed bags, and focus mitts. Participants will not make contact with each other while boxing. Participants can pace themselves during the training sessions and take rest breaks as needed. The exercise sessions will end with a 15- to 20-minute cool-down that will emphasize core stretching and breathing exercises.

**Table 1. Sample balance training activities focused on domains of balance dysfunction**

Domain 1 (trainer #1): Quiet Stance	Domain 2 (trainer #2): Reactive Postural Adjustments	Domain 3 (trainer #3): Anticipatory Postural Adjustments	Domain 4 (trainer #4/head): Dynamic Postural Control
Quiet stance w/ eyes open or eyes closed	Lean and release	Lower extremity reach (cone) training	Step initiation with light tracking resistance
Weight shifting	Pull test training	Standing and reaching	Ascending/Descending stairs
Sitting on stability ball w/rhythmic stabilization	Perturbation training in dual/single limb support	Gait initiation with resisted progression	Gait training with resisted progression

#### 10.3.4 Outcome Measures

Outcome assessments will take place at baseline (i.e., approximately 1 week before the beginning of the training program (T0)), at 6 weeks (T6), and 1 week after the completion of the 12 week training program (T12), as well as 3 months after the training program. All of the outcome assessments up to T12 will be performed by the PI at the Exercise Science Lab while the participants are on their standard course of medication. Motor dysfunction will be assessed at baseline using the motor section of the Unified Parkinson's Disease Rating Scale (UPDRS). The functional balance outcomes include: the mini BEST test (results of which will be shared with trainers at the YMCA for group assignment), the Activities-Specific Balance Confidence (ABC) scale, the Berg Balance Scale (BBS), the Timed Up and Go (TUG), and the Functional Reach Test (FRT). The kinematic outcomes from the hips, knees, and ankles of both limbs will be gathered using the VSTBalance during a straight line gait assessment at a self-selected pace. The infrared camera will identify the length of each lower-extremity segment (femur, tibia, foot) to derive the precise angular displacement (range of motion) occurring at the hip, knee, and ankle joints of each limb.

For Aim #1 we will be assessing the relationship between modifiable factors and outcomes on mobility assessments. We will compare individual characteristics as follows to identify if they are related to the balance outcomes in our model: gait characteristics (stride length, step length etc), motor dysfunction on UPDRS, lower-extremity joint kinematic range of motion, and balance domain dysfunction at baseline. For Aim #2 we will be asking individuals at baseline to self-report the number of falls they have had during the previous 3 months. We will send a prepaid postcard in the mail 3 months after the completion of the training intervention, asking participants to report the number of falls they have experienced since the training ended.

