#### 10.3.6 Sample size and Statistical analysis

Aim# 1 is the primary aim and based on our preliminary data with alpha=.05, a sample size of 20 will give 84% power to detect a relationship with an effect size of  $r=.60$ . The prevalence of PD in industrialized countries is estimated to be about 0.3%. Using this estimation, we anticipate there to be approximately 2,129 persons in the Boise area with PD. Based on these factors we anticipate fully meeting our recruitment needs.

For Aim #1, the goal is to explore the relationship between modifiable factors and outcomes. Initially because of the exploratory nature of these explorations, change scores for the outcome measures will be

constructed. Bi-variate correlations, parametric and non-parametric as appropriate, will be used to assess the strength of the relationship between individual outcome change scores and the modifiable factors. These results may be confounded by the progression of the disease, especially at the later measurement. Change in disease state will be introduced as a possible influence in partial correlations between modifiable factors and outcomes. Effect sizes will be calculate using Cohen's  $d$ .

For Aim #2 the interest is in the reduction of falls among this patient population. Initially to examine the changes in the number of falls a non-parametric McNemar test of change will be used. To examine other factors outside of the intervention that could influence the outcome will follow-up the analyses with McNemar test stratified by possible confounders (i.e. progression of the disease, continuation of the exercise regimen).

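### The two fall reports compared in Aim #2 differ in mode and slightly in window, and no procedure is described for postcards that are not returned

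*Protocol*

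**What the plan says.** **Baseline.** At the day-one laboratory visit (Protocol 10.3.3), participants are asked verbally, along with the demographic items, for the "number of falls experienced over the past 3 months". Section 10.3.4 repeats this for Aim #2: participants are to "self-report the number of falls they have had during the previous 3 months".

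**Follow-up.** In-person assessment stops at T12: "All of the outcome assessments up to T12 will be performed by the PI at the Exercise Science Lab". For falls, 10.3.4 then has a prepaid card go out by post once 3 months have passed since training finished, "asking participants to report the number of falls they have experienced since the training ended". The postcard is the only procedure described for the 3-month time point. Neither document mentions a closing date for the question, a completion date, a return deadline, a reminder, or a rule for cards that do not come back.

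**Analysis.** Protocol 10.3.6 and the SAP plan a McNemar test of the change in falls, followed by a "McNemar test stratified by possible confounders (i.e. progression of the disease, continuation of the exercise regimen"). The 20% allowance in Protocol 10.4 is for dropout, set against the sample of 20 that was sized for Aim #1. Card non-return is not mentioned.

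**The concern.** The study describes one intervention group, and 10.5 leaves a randomized comparison to a later application. With no control arm, any difference in how falls are measured before and after training does not cancel and is read as part of the training effect. Three differences matter here:

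- **Window.** Baseline covers a fixed 3 months. Follow-up starts when training ends and closes when the card is filled in.
- **Mode.** Baseline is a spoken answer in person; follow-up is a mailed card.
- **Non-return.** McNemar uses complete pairs only. If returning the card depends on having fallen after training, the pairs that remain are a selected set.

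Separately, continued exercise is a named stratifier, but neither document says how or when it is collected.

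Protocol 10.4 proposes to fall back on effect sizes if results are not significant. That gives no protection, because an effect size from the same data carries the same bias.

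**Working it through.** **The plan's own figure.** None exists for Aim #2: the documents give no power, fall rate or return rate. The only power figure, 84% for Aim #1 (n = 20, r = 0.60, alpha 0.05), is reproduced at 83.5% by two-sided simulation under the bivariate normal model. It has no bearing on falls.

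**Inputs.** From the documents: 3-month windows (taken as 13 weeks), 20 completers, a paired McNemar test. Assumed: falls are reduced to any versus none, and all fall rates, delays and return rates below.

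**1. Window.** Exposure ratio = (13 + w)/13 for a card completed w weeks after mailing: 14/13 = 1.08, 15/13 = 1.15, 17/13 = 1.31.

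Share with any fall, negative binomial with mean m and shape k = 0.5: 1 − (1 + m/k)^(−k). With a mean of 1 fall per 13 weeks and no true change:

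| Delay | m | Share with any fall |
|---|---|---|
| 0 weeks | 1.000 | 42.3% |
| 1 week | 1.077 | 43.7% |
| 2 weeks | 1.154 | 45.0% |
| 4 weeks | 1.308 | 47.4% |

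In 20 people, 2 to 4 weeks' delay adds 20 × 0.027 = 0.5 to 20 × 0.051 = 1.0 faller. Protocol 10.4 expects few baseline fallers; with a mean of 0.2, a 2-week delay moves 15.5% to 17.3%, or 20 × 0.018 = 0.4 of a person. The error always works against showing a reduction.

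**2. Non-return, complete pairs.** Suppose 40% fall at each time (no true change), a proportion b fall at both, and cards come back from 60% of post-training fallers and 90% of non-fallers.

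- Returned overall: 0.4 × 0.6 + 0.6 × 0.9 = 0.78.
- Follow-up share among returners: 0.24/0.78 = 30.8%.
- Baseline share among returners: [0.6b + 0.9(0.4 − b)]/0.78 = (0.36 − 0.3b)/0.78.
- Discordant cells: baseline-only fallers 0.9(0.4 − b), follow-up-only fallers 0.6(0.4 − b). The ratio is 0.9/0.6 = 1.5 whatever b is, provided discordant pairs exist.
- Expected excess of baseline-only over follow-up-only pairs among 20 completers: 20 × 0.3 × (0.4 − b).

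| Fall at both times (b) | Baseline share | Follow-up share | Apparent relative reduction | Excess pairs |
|---|---|---|---|---|
| 16% (independent) | 40.0% | 30.8% | 23% | 1.4 |
| 25% | 36.5% | 30.8% | 16% | 0.9 |
| 30% | 34.6% | 30.8% | 11% | 0.6 |
| 40% (same people) | 30.8% | 30.8% | 0% | 0 |

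If fallers were instead the more likely to reply (90% against 60%), the tilt would be 1.5 to 1 the other way.

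**3. Precision.** Non-return of 10%, 20%, 30% or 40% leaves 18, 16, 14 or 12 pairs from 20. If 30% change from faller to non-faller and 5% the reverse (assumed), exact two-sided McNemar power is 32% with 20 pairs, 20% with 16, 14% with 14 and 8% with 12.

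**4. What missing cards leave unknown.** With 6 fallers on 16 returned cards and 4 missing (assumed), the share among all 20 lies between 6/20 = 30% and 10/20 = 50%.

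**The case against.** The strongest reply is that little separates the two reports. Both are retrospective self-reports, and mailing at 3 months makes the follow-up window nominally equal to the baseline one. This stands: a reader might infer an unlimited window, but the excess is only mailing and completion delay, probably weeks, and it is conservative.

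A reader might also infer that non-return alone would create a 23% reduction. That figure compares returners with the full baseline sample. In the planned paired test a missing card removes the baseline value too, so 23% arises only if falls before and after are independent within a person. Some dependence is more plausible, and the figure then shrinks, to 0% if the same people fall both times. The return rates, and the direction of selection, have no support in the documents. Nor is it shown that these errors would decide Aim #2. The expected shift is at most 1.4 pairs in the cases tabulated, whereas an exact two-sided McNemar test needs at least six discordant pairs, all in one direction, to reach 0.05 (2 × 0.5^6 = 0.031; five give 2 × 0.5^5 = 0.063).

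On continued exercise, the plan to stratify by it suggests the investigators mean to collect it. The card is not reproduced and section 10.6 shows no content in the public text. That the variable is never recorded, or the stratified test impossible, would be an inference from silence.

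Finally, telephone calls bring their own drawback: an interviewer may influence answers after a program that participants know they received, and a call is still not the in-person baseline question.

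What survives is that the documents offer no means of detecting or bounding selective non-return, in a design where it does not cancel.

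**Conclusion.** The concern holds in limited form. The mode differs, the follow-up window has no stated end, and no contact with non-returners is described. The window error is small (about 0.5 to 1 person in 20 for a 2- to 4-week delay at the higher assumed fall rate, less at a lower one) and works against a reduction. Non-return matters more because its direction is unknown: under the assumed 60%/90% return rates, the discordant cells tilt 1.5 to 1 toward a reduction, and the apparent relative reduction is 0% to 23% as the share falling at both times goes from 40% down to 16%. No size can be put on the mode difference from the documents. For continued exercise, the supportable statement is that no collection is described. Aim #1 is the primary aim, so this is a modest and inexpensive improvement that does not threaten the study's main result.

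**What to change.** In Protocol 10.3.4:

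- Word the card to ask for falls between the training end date and a stated date 3 months later, and ask for the date of completion.
- Telephone anyone whose card has not arrived within 2 weeks and ask the same dated question, recording that the answer came by telephone. A late answer then no longer lengthens the window, though recall is a little longer.
- Add one yes/no item on continued exercise.

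In Protocol 10.3.6 and the SAP: report the number of unreturned cards, and give the McNemar result twice more, counting every missing participant first as a post-training faller and then as a non-faller. An adjustment for days at risk is not needed, since the plan has no count model.

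Cost: a few short calls by existing staff (at most 24 participants, with contact details already taken on day one), a mixed reporting mode for those called, and a minor amendment. Treatment, visits and sample size are unchanged. Replies and exercise status may not be reliably recoverable once the follow-up period has passed, so the change should be made before cards go out.

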#### 10.3.5 Participants

Individuals with mild to moderate idiopathic PD will be recruited through various mechanisms including, PD support groups throughout the Treasure Valley (see support letter), the Movement Disorders Clinic at St. Luke's Medical Center (see support letter), the Neurology clinic at St. Alphonsus hospital, the VA Medical center, and through word of mouth from current participants already enrolled in the exercise program.

Inclusion Criteria: A diagnosis of idiopathic PD; Male or female ages 50-65, 30 years or older at time of PD diagnosis; Hoehn & Yahr (H&Y) stages 1.0-3.0; Ability to provide informed consent in accordance with Good Clinical Practice (GCP) and local regulations. Exclusion Criteria: Idiopathic PD H&Y stage 4-5, in order to constrain motor dysfunctions to mild-to-moderate PD; Confirmed or suspected atypical parkinsonian syndromes due to drugs, metabolic disorders, encephalitis, or degenerative diseases; Presence of definite dementia by Montreal Cognitive Assessment (MoCA <21); Central or peripheral nervous system disorders (other than PD); Myopathic disease (e.g. focal myopathy) that affects skeletal muscle structure/function; Severe cardiovascular disease that limits exercise abilities.

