**Table 2. Predictors of improvements in functional mobility**

Predictors	Modifying factor	Interpretation
Motor dysfunction	Higher UPDRS scores (more advanced PD)	We expect that mobility improvements will be greatest in individuals with more advanced UPDRS stages.  This may be due to decreased economy of movement in persons with more advanced PD. 
Balance domain dysfunction at baseline	Domain 3: Anticipatory postural control	Based on our preliminary data  we expect that individuals with anticipatory postural control deficits will see the greatest improvements in function
Knee and ankle joint angular displacement during gait	Peak joint angular displacement (range of motion)	Increases in peak knee and ankle angular displacement after exercise suggest that individuals with PD may move with greater flexibility and confidence 

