## 10.4 Potential Problems & Alternative Approaches

One potential problem with this clinical trial is that dropouts may occur. Our prior experience with longitudinal exercise studies suggests that we can expect a dropout rate between 5-20%. We have anticipated a very conservative 20% rate, and will recruit 4 additional participants over our sample size of 20. This will ensure an appropriate number of subjects completing the study to maintain the desired statistical power.

While we are attempting to limit the variability in participant outcomes by constraining inclusion criteria to persons with mild to moderate PD, this also poses a challenge in that many participants who volunteer for exercise studies are likely to be physically active individuals, which has the potential to dilute our treatment effect. This recruitment bias may also mean that few of these individuals will have experienced falls at baseline. In the event that non-statistically significant results appear, we have planned our analysis such that we can utilize clinically significant outcomes (eg., effect sizes) to overcome any potential recruitment bias and demonstrate the clinical impact of the intervention.

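### On the mini BEST, BBS and ABC, a maximum score can create or inflate the expected link between higher UPDRS and greater improvement, and the Aim #1 analysis has no check for it

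*Protocol*

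**What the plan says.** Protocol 10.3.5 admits "Hoehn & Yahr (H&Y) stages 1.0-3.0". On disease stage it excludes only the severe end: "Idiopathic PD H&Y stage 4-5, in order to constrain motor dysfunctions to mild-to-moderate PD". It sets no minimum balance deficit, mini BEST score or fall history. Protocol 10.4 expects that "many participants who volunteer for exercise studies are likely to be physically active individuals, which has the potential to dilute our treatment effect".

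Protocol 10.3.4 takes the UPDRS motor section at baseline. The functional balance outcomes are the mini BEST, the ABC, "the Berg Balance Scale (BBS), the Timed Up and Go (TUG), and the Functional Reach Test (FRT").

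The analysis is in 10.3.6, with the same text in the protocol and the SAP. It makes Aim #1 primary and says that "change scores for the outcome measures will be" constructed and then correlated one by one with the modifiable factors. The only adjustment named is a partial correlation for change in disease state. Neither the baseline score nor a scale maximum is mentioned.

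Table 2 gives the expected result: "We expect that mobility improvements will be greatest in individuals with more advanced UPDRS stages".

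**The concern.** Change on a bounded scale is cut off at the top. If milder patients have better balance, the cut falls mainly on those with low UPDRS. Their recorded change is then too small, while patients with higher UPDRS show their full gain. The correlation of UPDRS with change becomes positive although the true benefit is the same for everyone.

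That is the direction Table 2 predicts, so the artefact would look like confirmation. Protocol 10.3.7 intends to use these findings to target rehabilitation to individual risk factors, so the misreading would carry forward.

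Two provisions in the plan might seem to cover this, but neither does. Adjusting for change in disease state does not remove the artefact, because the cut-off depends on where a participant starts on the scale, not on how far the disease has moved. The remedy in 10.4 for active volunteers is to rely on effect sizes, and an effect size computed from cut-off change scores carries the same distortion.

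**Working it through.** **Step 1: the plan's own figure.** Inputs from 10.3.6: n=20, alpha .05, r=.60, stated power 84%.
- Fisher z, two-sided: atanh(.60)=.693; .693×√17=2.858; 2.858−1.960=0.898; Φ(0.898)=81.5%.
- Simulation from a bivariate normal (200,000 runs): 83.5%.

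The stated 84% is reproduced. The two-sided critical value at n=20 is |r|=√(t²/(t²+18))=.444, where t is the 97.5th percentile of t on 18 df.

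**Step 2: inputs for the ceiling check.** Only n, alpha and the upper value for the gain come from the documents. The rest are assumptions.
- Gain 0.5 to 0.66 baseline SD, unrelated to severity. The value 0.66 is the pilot d in 10.3.1 (n=5), reported next to the TUG result and not for a bounded scale.
- Severity–balance correlation (absolute value) 0.4 to 0.6.
- Score reliability 0.90.
- Share at the maximum at T0: 0, 10, 20 or 30%.
- That the mini BEST, BBS and ABC have a fixed maximum is taken as a property of the instruments. The documents give no score ranges.

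**Step 3: model.** Let S be standardised severity and B=−ρS+√(1−ρ²)·e the true balance. The baseline score is min(c, B+error) and the follow-up score is min(c, B+gain+error). The limit c is set to give the assumed share at the maximum. Change is follow-up minus baseline, and r is the Pearson correlation of S with change.

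**Step 4: results for an identical gain of 0.66 SD (n=20, 30,000 runs per cell).** The significance rate is the rate in the predicted direction plus the rate in the opposite direction.

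| At maximum at T0 | Mean r, ρ=0.4 | Significant | Mean r, ρ=0.6 | Significant |
|---|---|---|---|---|
| 0% | .00 | 2.5+2.4=4.9% | .00 | 2.4+2.6=5.0% |
| 10% | .13 | 8.0+0.6=8.6% | .20 | 13.6+0.2=13.8% |
| 20% | .19 | 12.9+0.3=13.2% | .29 | 24.2+0.1=24.3% |
| 30% | .22 | 15.5+0.2=15.7% | .33 | 31.0+0.0=31.0% |

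Over the whole assumed range (gain 0.5 to 0.66 SD, with the gain also allowed to vary between people), repeated simulations put mean r at about .1 to .3 and the false-positive rate at about 7 to 33%. Nearly all the excess lies in the predicted direction. Stronger assumptions give more: ρ=0.8 and reliability 0.97 with 30% at the maximum give mean r .59. The conclusion does not rely on that case.

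**Step 5: no average gain.** With gain 0 and 30% at the maximum, mean r is about 0 and about 2% are significant in each direction. The artefact disappears.

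**Step 6: leaving out those at the maximum at T0.** In the Step 4 range, mean r falls to about .04 to .15 and the false-positive rate to about 5 to 9%. Some bias remains because participants just below the limit are still cut off at follow-up. With 10, 20 and 30% removed, the expected n is 20×0.9=18, 20×0.8=16 and 20×0.7=14. The Fisher z formula of Step 1 at r=.60 then gives:
- n=18: .693×√15−1.960=0.72, power 77%
- n=16: .693×√13−1.960=0.54, power 71%
- n=14: .693×√11−1.960=0.34, power 63%

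**The case against.** The strongest reply is that the inputs cannot be verified. The documents give neither a baseline distribution nor a share at the maximum for any scale. At the mild end of the assumptions (10% at the maximum, the smaller gain), mean r is about .10 and the false-positive rate 7%, which is little more than nominal. This stands. It is why the point asks for the share to be reported and does not claim that the result will be wrong.

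Second, Table 2 speaks of mobility, and the pilot improvement in 10.3.1 is on the TUG, a time in seconds. TUG and FRT have no fixed maximum score, so the concern does not reach them in the same way. This also stands. But 10.3.4 lists all five outcomes, and 10.3.6 does not confine the UPDRS correlation to TUG and FRT. Good performers may have less room to improve on those two tests as well, so agreement with them supports a claim without proving it.

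Third, 10.3.6 calls Aim #1 exploratory, and a wide severity range helps a correlation with severity. That is a fair reason to leave eligibility alone. It is not a reason to leave the correlation unchecked.

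A reader might also infer that the assignment rule fails for people at H&Y 1.0. The rule is that "each individual is assigned to work on activities focused on their area of greatest deficiency in the four balance domains", based on "the mini BEST test (results of which will be shared with trainers at the YMCA for group assignment"). Greatest deficiency is a relative ranking, so anyone with unequal domain scores can be placed. The rule is silent only where no domain is deficient or the weakest domains tie, and nothing in the documents shows that H&Y 1.0 implies either.

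**Conclusion.** The concern holds in a conditional form. On the mini BEST, BBS and ABC, a positive correlation of baseline UPDRS with raw change cannot by itself be read as more advanced patients benefiting more. An equal benefit for everyone, cut off at the scale maximum, gives the same pattern. Under the stated assumptions the spurious mean r is about .1 to .3, against a critical value of .444 and a planned r of .60, and the false-positive rate is about 7 to 33% instead of 5%.

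Three conditions are needed: a real average gain, an association between milder disease and better balance, and a material share of participants at or near the maximum. The plan expects the first. The documents establish neither the second nor the third.

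A reader might infer that a ceiling alone would produce the Table 2 result. It would not: without an average gain the mean r is about 0. A reader might also infer that eligibility must change. The documents do not support that either. Requiring one mini BEST domain below its maximum would leave the BBS, the ABC and near-maximum scores untouched.

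**What to change.** Add to 10.3.6 in the protocol and the SAP:
- For the mini BEST, BBS and ABC, report the number and share of participants at the scale maximum at T0 and at each follow-up.
- For each of these scales, give the UPDRS–change correlation with a confidence interval, with and without participants at the maximum at T0.
- Interpret a positive correlation as greater benefit in more advanced disease only if it persists without those participants and is consistent with TUG and FRT change. Code all changes so that a positive value means improvement.

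The cost is a few sentences and no new data. The restricted analysis has fewer than 20 participants and less precision (Step 6), so loss of significance alone should not count as failure to persist. The estimates should be compared with their intervals. The restriction reduces the artefact without removing it.

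Eligibility need not change. How to assign participants with no deficient domain or with tied domains is for the investigators to settle.
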